1. BACKGROUND AND RATIONALE

1.1 Background

An increased incidence of cardiovascular events has been observed at higher hemoglobin (Hb) levels in recently published studies of anemia correction in patients with chronic kidney disease (CKD) not on dialysis [1, 2]. These studies failed to demonstrate that correction of anemia to a target Hb of 13.5 g/dL or higher in patients with chronic kidney disease not receiving dialysis reduces the risk of cardiovascular events. One study suggested that this degree of correction of Hb level may be associated with an increased risk without incremental improvement in quality of life. Taken together, these findings suggest caution in the full correction of anemia in patients with chronic kidney disease.

The global clinical development program for MIRCERA® included 13 Phase I clinical pharmacology studies and 10 therapeutic studies comprising four Phase II and six Phase III studies in patients with CKD, including patients on dialysis and not on dialysis. Administration of MIRCERA® for the treatment of anemia associated with CKD was generally well tolerated with no difference in the safety profile in comparison to reference erythropoiesis stimulating agents (ESAs) [3, 4].

Data from phase III correction studies show that the Hb response rates in the MIRCERA® group at the end of the correction period were high (93.3% and 97.5% in the studies in patients on dialysis and not on dialysis, respectively) and comparable to comparators (91.3% and 96.3%, respectively). The median time to response was 43 days in the MIRCERA® arm and 29 days in the comparator arm with increases of hemoglobin within the first 6 weeks of 0.2 g/dl/week and 0.3 g/dl/week, respectively.

Four randomized controlled phase III studies were performed in dialysis patients currently treated with darbepoetin alfa or epoetin. Patients were randomized to stay on their current treatment or to be converted to MIRCERA® in order to achieve stable hemoglobin levels. At the evaluation period (week 29-36), the mean and median level of hemoglobin in patients treated with MIRCERA® was virtually identical to their baseline hemoglobin level.

1.1.1 Study Drug

Methoxy polyethylene glycol-epoetin beta (MIRCERA®) is a covalent conjugate of a protein produced by recombinant DNA technology in Chinese Hamster Ovarian cells and conjugated to a linear methoxy-polyethylene glycol (PEG). MIRCERA® is a continuous erythropoietin receptor activator that shows a different activity at the receptor level characterized by a slower association to and faster dissociation from the receptor, a reduced specific activity in vitro with an increased activity in vivo, as well as an increased half-life, in contrast to erythropoietin. The average molecular mass is approximately 60 kDa of which the protein moiety plus the carbohydrate part constitutes approximately 30 kDa.

MIRCERA® stimulates erythropoiesis by interaction with the erythropoietin receptor on progenitor cells in the bone marrow. As primary growth factor for erythroid development, the natural hormone erythropoietin is produced in the kidney and released into the bloodstream in response to hypoxia. In responding to hypoxia, the natural hormone erythropoietin interacts with erythroid progenitor cells to increase red cell production.

The approved reference ESA compounds in the study will be darbepoetin alfa (Aranesp®, Nespo®, Aranest®), epoetin alfa (Eprex®, Epogen®, Epopen®, Erypo®) and epoetin beta (NeoRecormon®, Recormon®).

1.2 Rationale for the Study

As part of the risk management plan, Roche proposes to gain more experience with MIRCERA® administered under clinical practice conditions and according to the approved label by performing a non-inferiority study comparing MIRCERA® to other ESAs in terms of mortality and cardiovascular morbidity.

2. OBJECTIVES

2.1 Primary Objective

The primary objective is to demonstrate non-inferiority of MIRCERA® versus reference ESAs in terms of a composite endpoint of all-cause mortality and non-fatal cardiovascular events (myocardial infarction (MI), stroke).

2.2 Secondary objectives

The secondary objectives are to assess the incidence of anti-erythropoietin antibody-mediated pure red cell aplasia (PRCA), gastrointestinal bleeding and thromboembolic events.

[figure not shown]
3. STUDY DESIGN

3.1 Overview of Study Design and Dosing Regimen

The study will be a randomized, controlled, open-label, multi-centre parallel group, non-inferiority trial comparing MIRCERA® to other ESAs.

The total length of the study *was* estimated to be 4 years (30 months recruitment and 18 months *of* follow-up on treatment after last patient randomized) until the pre-specified number of outcome events *were* recorded. *Due to an event rate lower than anticipated, it is expected that the study will be prolonged by approximately 4-6 years.*

Figure 1 Study Design

After written informed consent is obtained, patients will be screened for eligibility. Providing all eligibility criteria are met, patients with renal anemia not treated with an ESA will be randomly allocated 1:1 either to MIRCERA® once every two weeks (group A) or to a reference ESA treatment (group B) according to label for correction of their renal anemia. Once corrected, MIRCERA® patients should be treated with once monthly administration. Patients with renal anemia on stable maintenance ESA therapy will be randomized 1:1 to continue their current ESA treatment (group B) or to change to MIRCERA® treatment (group A) once-monthly.

3.1.1 Rationale for Study Design

1264 events are sufficient to ensure 90% power to establish non-inferiority of MIRCERA® to comparator ESAs in terms of the composite endpoint based on a non-inferiority margin of 1.20 and a one-sided significance level of 0.025, assuring that the maximum difference between groups at the upper limit of the CI would be 6.1 % for the composite endpoint and 3.6% for mortality.

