1264 events are sufficient to ensure 90% power to establish non-inferiority of MIRCERA® to comparator ESAs in terms of the composite endpoint based on a non inferiority margin of 1.20 and a one-sided significance level of 0.025, assuring that the maximum difference between groups at the upper limit of the CI would be 6.1 % for the composite endpoint and 3.6% for mortality.

Duration (months)	NI limit (HR)	Event rate per year	No. events / Nb patients	Expected Event rate at end of study (%)	Highest event rate based on NI limit (%)	Absolute / relative difference (%)	Absolute and relative difference in deaths (%)
48	1.2	0.2	1264 / 2800	45.2	51.2	6.1 / 13	3.6 / 13

Note: The overall event rate observed during the study is considerably lower than that expected at the planning stage. Changing no other parameters leads to an extended study duration; the occurrence of 1264 events has been estimated to be approximately 10 years after study start.

References

1. K/DOQI Clinical Practice Guidelines for Chronic Kidney Disease: Evaluation, Classification, and Stratification. Guideline 4: Evaluation of GFR. Am J Kidney Dis 2002, In: http://www.kidney.org/professionals/kdoqi/guidelines_ckd/p5_lab_g4.htm (accessed Aug 3rd 2006).
2. Cheung AK et al. Cardiac diseases in maintenance hemodialysis patients: Results of HEMO study. Kidney Int 2004;65:2380-2389
3. Excerpts from the USRDS. 2004 Annual Data Report: Atlas of end-stage renal disease in the United States. Am J Kid Dis 2005; 45: Suppl 1
4. Enkoyan G et al. Effect of dialysis dose and membrane flux in hemodialysis. New Engl J Med 2002; 347: 2010-2019

GLOSSARY OF ABBREVIATIONS

AE	Adverse event
BP	Blood pressure
CI	Confidence interval
CKD	Chronic Kidney Disease
CRP	C-reactive protein
CrCl	Creatinine clearance
DCS	Data collection specification
DSMB	Data and Safety Monitoring Board
dL	Deciliter
ECG	Electrocardiogram
eCRF	Electronic Case Report Form(s)
EDC	Electronic Data Capture
eform	Electronic form (page)
ESA	Erythropoiesis-Stimulating Agent
GFR	Glomerular Filtration Rate
Hb	Hemoglobin
HD	Hemodialysis
ICH	International Conference on Harmonization
iDCC	Independent Data Coordinating Center
ITT	Intention-to-treat
IVRS	Interactive Voice Response System
IMP	Investigational Medicinal Product
IU	International Unit
iv	Intravenous
kg	Kilogram
L	Liter
MDRD	Modification of Diet in Renal Disease
µg	Microgram
mL	Milliliter
µmol	Micromole
MI	Myocardial Infarction

GLOSSARY OF ABBREVIATIONS

min	Minute

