8.2.2 Sample Size

The randomization will be stratified by treatment setting (correction/maintenance) and baseline CRP category (≤ 30 mg/L / >30 mg/L). The stratification will ensure that 20% of patients will be recruited in the correction setting and 80% in the maintenance switch setting.

The expected yearly event rate is approximately 20%, based on

- an expected 25% composite endpoint rate (a mortality rate of approximately 16% [15, 16] and non-fatal cardiovascular morbidity of approximately 9% [17]) in the maintenance setting (80% of patients)
- a 7% rate for the combined endpoint in the correction setting (20% of patients) [CSR BA16738]

Assuming linear recruitment over 30 months and a follow-up time of 18 months after randomization of the last patient, a sample size of 2800 patients, representing approximately 7700 patient-years of exposure, would be adequate to observe 1264 events of the composite endpoint of death and non-fatal cardiovascular events.

1264 events are sufficient to ensure 90% power to establish non-inferiority of MIRCERA® to comparator ESAs in terms of the composite endpoint based on a non-inferiority margin of 1.20 and a one-sided significance level of 0.025.

Duration (months)	NI limit (HR)	Event rate per year	No. events / Nb patients	Expected Event rate at end of study (%)	Highest event rate based on NI limit (%)	Absolute / relative difference (%)	Absolute and relative difference in deaths (%)
48	1.2	0.2	1264 / 2800	45.2	51.2	6.1 / 13	3.6 / 13

Note: The overall event rate observed during the study is considerably lower than that expected at the planning stage. Changing no other parameters leads to an extended study duration; the occurrence of 1264 events has been estimated to be approximately 10 years after study start.

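### The 3.6-point maximum mortality difference is too small for all-cause death: it matches about 60% of the first-event composite difference, and the plan's own inputs give about 4.4 to 5.0 points at a death HR of 1.20

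*Combined protocol and SAP*

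**What the plan says.** Section 3.1.1 states that "1264 events are sufficient to ensure 90% power to establish non-inferiority of MIRCERA® to comparator ESAs in terms of the composite endpoint", with a "margin of 1.20 and a one-sided significance level of 0.025", and adds that "the maximum difference between groups at the upper limit of the CI would be 6.1 % for the composite endpoint and 3.6% for mortality". The sample-size part of the synopsis repeats "6.1 % for the composite endpoint and 3.6% for mortality".

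The tables in the synopsis and in section 8.2.2 carry one row: 1264 events in 2800 patients, 45.2% expected, 51.2% at the limit, a composite difference of 6.1 / 13, and 3.6 / 13 in the column headed "Absolute and relative difference in deaths".

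Section 8.2.2 gives the rates. "The expected yearly event rate is approximately 20%, based on" 25% a year in the maintenance setting (80% of patients) and 7% in the correction setting (20%). The 25% is made up of "a mortality rate of approximately 16" percent and non-fatal cardiovascular morbidity of about 9%. The correction-setting rate is not split into deaths and non-fatal events. Nowhere is the 3.6 derived.

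**The concern.** Section 8.1.1 defines the composite by whichever event comes first. A patient who has a non-fatal stroke and later dies contributes the stroke to the composite, not the death. All-cause mortality, and the secondary endpoint time to death in section 8.1.2, count that death. A fixed fraction of the composite difference is therefore not the difference in mortality.

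The relative difference points the same way. For a fixed hazard ratio, a lower cumulative risk gives a larger relative difference. Deaths are rarer than composite events, so their relative difference at HR 1.20 should exceed the composite's 13%. The table shows 13% for both.

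This is a post-authorization safety study with death in its primary endpoint. Anyone judging whether a margin of 1.20 is acceptable will look at the absolute excess in deaths that it allows, and the figure offered is too small.

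**Working it through.** **Inputs** (section 8.2.2 unless noted): linear recruitment over 30 months plus 18 months, so follow-up T is uniform on 1.5 to 4 years; pooled rate 0.2 a year; HR limit 1.20; 1400 patients per arm (section 3.2).

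**Formula.** With constant hazard h, the probability of an event by study end is F(h) = 1 − [exp(−1.5h) − exp(−4h)] / (2.5h).

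**Step 1: reproduce the composite.** Read 20% as an annual risk: h = −ln(0.8) = 0.2231.
- F(0.2231) = 1 − (0.7155 − 0.4096)/0.5579 = 45.16%; 2800 × 0.45158 = 1264.4 events.
- F(1.2 × 0.2231) = 1 − (0.6692 − 0.3426)/0.6694 = 51.22%.
- Difference 6.06 points; relative 6.06/45.16 = 13.4%.

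All the stated composite figures match.

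**Step 2: look for the 3.6.**
- Scaling: the stratum rates give a composite of 0.8 × 25 + 0.2 × 7 = 21.4, and maintenance deaths are 0.8 × 16 = 12.8. Then 6.06 × 12.8/21.4 = 3.62, and the relative difference stays at 13.4%. Both table entries match. Any death share from 0.586 to 0.602 also rounds to 3.6; a share of 16/25 = 0.64 gives 3.88.
- HR 1.20 applied directly to mortality: 3.6 points needs an annual mortality of about 8.3% (21% cumulative), and the relative difference would be 17%. Maintenance deaths alone already give 12.8% overall.

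Scaling fits and direct application does not. This is an inference from the match.

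**Step 3: all deaths, on the pooled basis of the 6.1.** Take deaths as a share s of the composite hazard, unchanged after a non-fatal event, with a death HR of 1.20.

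| s | death hazard | reference | at HR 1.20 | difference | relative |
|---|---|---|---|---|---|
| 0.60 | 0.1339 | 30.48% | 35.28% | 4.80 | 15.8% |
| 0.64 | 0.1428 | 32.12% | 37.10% | 4.98 | 15.5% |

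**Step 4: all deaths, on the stratum rates.** Maintenance hazard −ln(0.84) = 0.1744, weight 0.8; correction weight 0.2.

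| correction deaths per year (assumed) | reference | at HR 1.20 | difference | relative |
|---|---|---|---|---|
| 0 | 30.08% | 34.49% | 4.41 | 14.7% |
| 4.5% (0.64 × 7%) | 32.45% | 37.29% | 4.84 | 14.9% |

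Outside these cases: reading 16% as a hazard with no correction deaths gives 4.23, and treating every correction-setting event as a death gives 5.04. No reading tried gives 3.6 or 13%.

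**Step 5: patients.** 1400 × 0.036 = 50 excess deaths as stated; 1400 × 0.0441 = 62; 1400 × 0.0480 = 67; 1400 × 0.0498 = 70.

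**The case against.** The strongest reply is that the arithmetic is right and only the label is loose. If 3.6 is the deaths part of the 6.1-point composite difference, it is a valid quantity, and its place beside the composite column with the same 13% suggests that meaning. This stands to the extent that relabelling is an acceptable remedy. It does not rescue section 3.1.1 or the synopsis, which call the figure a maximum difference for mortality.

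A second reply is that the derivation is a guess. That is true, and a reader might go too far by concluding that the plan assumed no deaths in the correction setting. The documents do not support that conclusion: 12.8/21.4 is one share among those from 0.586 to 0.602 that round to 3.6, and correction mortality is not stated. The finding does not depend on it, because direct calculation exceeds 3.6 in every case tried.

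A third is that stratum-based deaths should not be set beside a pooled composite. This is right. On stratum rates the composite difference is 5.76 points, not 6.06, so a figure placed in the same row as 6.1 should use the pooled rate.

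A fourth is that the planning rates are superseded: the note in section 8.2.2 puts 1264 events at about 10 years. This too is fair, so any figure should be tied to the 48-month design. Prolongation does not restore 3.6. With the same 45.2% composite incidence reached at 8 to 10 years and a 60 to 64% death share, the difference is again 4.8 to 5.0 points.

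**Conclusion.** As a statement about mortality, 3.6 / 13 is wrong. On the plan's own inputs the difference is about 4.8 to 5.0 points (about 16% relative) on the pooled rate with deaths at 60 to 64% of the composite hazard, or about 4.4 to 4.8 points (about 15% relative) on the stratum rates with 0 to 4.5% annual mortality in correction. At a 60% share the stated value falls short by (4.80 − 3.6)/4.80 = 25%.

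This rests on a death hazard ratio of 1.20, constant hazards, a death hazard unchanged after a non-fatal MI or stroke, and the 48-month design. The documents give no figure for the hazard after a non-fatal event.

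Two stronger readings should be resisted. A reader might take 4.8 as the true bound on mortality. It is not: the confidence interval for the composite does not bound the hazard ratio for death, so neither 3.6 nor 4.8 is assured. A reader might also infer that the sample size or the test is faulty. The 1264 events, the 90% power, the 6.1 figure and the decision rule in sections 8.2.1.1 and 8.2.3 depend only on the composite and are unaffected.

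**What to change.** In section 3.1.1, the synopsis text and both tables, do one of the following.

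- Replace 3.6 / 13 with the all-cause death figure on the same pooled basis as the 6.1: about 4.8 points and about 16% relative at a 60% death share. State the share, the constant-hazard assumption and the treatment of deaths after a non-fatal event.
- Keep 3.6 / 13 and relabel it as deaths occurring as the first composite event, with the share used. The basis must be named here too. On stratum rates, first-event deaths differ by 3.3 points with no correction deaths, or 3.7 points with a 64% share in both strata.

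In either case, say that the figure is conditional on a hazard ratio of 1.20 for death and on the 48-month duration, and remove the claim that the composite confidence interval assures it. Record how the number was derived.

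The cost is one recalculation and a wording change. The design, the event target and the analysis stay as they are. If the number is replaced, the stated excess in deaths becomes less favourable.

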8.1.2 Secondary Endpoints

Secondary endpoints are the time to the individual components of the composite endpoint: the time to death, the time to non-fatal cardiovascular events (MI or stroke), the time to MI and the time to stroke.

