8.2 Statistical and Analytical Methods

8.2.1 Statistical Model

8.2.1.1 Primary Endpoint

The analysis of time to event endpoints is based on the survivor function, which is the probability to survive or, more generally, to remain event-free beyond a certain point in time. The primary endpoint will be analyzed with a Cox's proportional hazards model to estimate the hazard ratio and its 95% confidence interval between the two treatment groups. The underlying proportional hazards model is $\lambda(t) = \lambda_0(t)\exp(\beta Z)$. Thereby, β is the coefficient corresponding to the binary vector Z taking the value 0 for patients on the reference arm and the value 1 for patients on the MIRCERA® arm, and $\lambda_0(t)$ is the baseline hazard of the reference treatment. Based on this, the following non-inferiority hypothesis for the hazard ratio ($h_{MR} = \exp(\beta)$) between MIRCERA® and reference will be tested by comparing the upper limit of the 95% confidence interval for the hazard ratio to 1.20:

$$H_0: h_{MR} \geq 1.20 \quad \text{versus} \quad H_1: h_{MR} < 1.20$$

The null hypothesis will be rejected if the upper limit of the confidence interval is below 1.20. The underlying Cox regression model will retain treatment as factor.

In addition, analyses based on Cox models adjusted for the baseline stratification factors and other clinically relevant baseline variables such as CRP at screening, age and baseline risk factors will be reported.

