8.2.1.2 Secondary Endpoints

Kaplan-Meier methods and frequency tables will be used to describe the time to the composite endpoint as well as the time to the individual components of the composite endpoint for the MIRCERA® versus reference group. The survival function will be summarized for the 25th percentile, the median, the 75th percentile and their 95% confidence intervals. The plot of Kaplan-Meier estimates for the two treatment groups will be presented. The un-stratified log-rank test will be used to compare survivor functions between the two treatment groups.

In addition, analyses based on Cox models adjusted for the baseline stratification factors (including CRP) and other clinically relevant baseline variables such as age and baseline risk factors will be reported.

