8.2.3 Hypothesis Testing

The primary endpoint is the time between first dose of study medication and the date of death or non-fatal cardiovascular events (MI, stroke), whatever occurs first. The hypotheses to be tested are:

$H_0: h_{MR} \geq 1.20$ versus $H_1: h_{MR} < 1.20$

Using the correspondence between tests and confidence intervals, the test for non-inferiority will be based on the upper limit of the two-sided 95% confidence interval for the hazard ratio of the two groups. When the upper confidence interval limit is lower than 1.20, the MIRCERA® group will be regarded as clinically non-inferior to the reference group. The corresponding p-value will be calculated via the standard normal distribution:

$$p = P(t \leq \hat{T}) = \Phi \left(\frac{\ln \hat{h}_{MR} - \ln 1.20}{SE} \right),$$

where SE denotes the standard error of $\ln \hat{h}_{MR}$ and Φ is the cumulative distribution function of the standard normal distribution.

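### The stated assurance of at most a 3.6% mortality difference does not follow from a test of the composite hazard ratio alone

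*Combined protocol and SAP*

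**What the plan says.** The synopsis (sample size part) and Section 3.1.1 state that 1264 events give 90% power for non-inferiority on the composite. They add, as something the design assures, that the "maximum difference between groups at the upper limit of the CI would be 6.1 % for the composite endpoint and 3.6% for mortality". The sample size tables in the synopsis and Section 8.2.2 carry a column headed "Absolute and relative difference in deaths" with the entry 3.6 / 13, next to 6.1 / 13 for the composite.

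The test itself is confined to the composite:

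- Section 2.1 sets the objective: "to demonstrate non-inferiority of MIRCERA® versus reference ESAs in terms of a composite endpoint".
- Section 8.2.1.1: "The null hypothesis will be rejected if the upper limit of the confidence interval is below 1.20". The HR in question is that of the composite.
- Section 8.2.3: "When the upper confidence interval limit is lower than 1.20, the MIRCERA® group will be regarded as clinically non-inferior to the reference group".
- Section 8.1.2: "Secondary endpoints are the time to the individual components of the composite endpoint: the time to death", with no margin attached.
- Section 8.2.1.2 plans Kaplan-Meier estimates, frequency tables and adjusted Cox models for the components, and: "The un-stratified log-rank test will be used to compare survivor functions between the two treatment groups". Section 8.2.6 adds a descriptive summary of deaths.

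**The concern.** A confidence limit on the composite HR bounds the composite. It bounds mortality only under extra conditions that the plan does not state. Two things break the link. The component HRs can differ, so that more deaths are offset by fewer MIs and strokes. And even with one HR for all components, there are fewer deaths than composite events, so the mortality estimate is less precise.

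This is a post-authorisation safety study, and death is the gravest component. A reader of the synopsis could take a positive result as having excluded a mortality excess above 3.6 percentage points, which the test does not do.

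**Working it through.** **Inputs from the plan.** 1264 events, 2800 patients, 1:1 allocation, margin 1.20, one-sided alpha 0.025, yearly event rate 20%, linear recruitment over 30 months plus 18 months of follow-up. Maintenance setting (80% of patients): 25% composite rate, made up of 16% mortality and 9% non-fatal events. Correction setting (20%): 7% composite rate.

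**Assumptions.** Constant hazards, no withdrawal, the original 48-month schedule, and a share s of first events that are deaths between 0.60 and 0.64. The 0.64 is the maintenance split 16/25. The 0.60 is inferred below.

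**1. The plan's figures.**
- Events: 4 × (1.960 + 1.282)² / (ln 1.2)² = 1264.4.
- Cumulative risk with follow-up uniform over 1.5 to 4 years: P(λ) = 1 − (e^(−1.5λ) − e^(−4λ)) / (2.5λ). With λ = −ln 0.8 = 0.2231, P = 45.16%. With 1.2λ, P = 51.22%.
- Difference 6.06 points, relative 13.4%. So 45.2, 51.2, 6.1 and 13 all reproduce.
- No derivation of 3.6 is given. The likely one is a death share times the composite difference: 0.8 × 16 / (0.8 × 25 + 0.2 × 7) = 12.8 / 21.4 = 0.598, and 0.598 × 6.06 = 3.62. This counts no deaths in the correction setting. The match and the repeated 13% make it plausible, but it remains an inference.

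Such a figure assumes HR 1.20 on every component and leaves out deaths after a non-fatal event.

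**2. Same HR on all components.**
- The standard error of the composite log HR is 2/√1264 = 0.0563. The largest estimate that passes is exp(ln 1.2 − 1.96 × 0.0563) = 1.075.
- If the mortality HR is also 1.075, its upper limit is exp(ln 1.075 + 1.96 × 2/√d). With d = 758 (0.60 × 1264) this is 1.24. With d = 943 it is 1.22. The 943 is all-cause deaths at 16% yearly mortality in maintenance and an assumed 7% in correction: 2800 × [0.8 × P(−ln 0.84) + 0.2 × P(−ln 0.93)].
- Power to exclude a mortality HR of 1.20 when the true HR is 1.00, Φ(ln 1.2 × √d/2 − 1.96), is 71% with 758 deaths and 80% with 943, against 90% for the composite.
- At a common HR of 1.20, the all-cause death difference P(1.2sλ) − P(sλ) is 4.80 points (s = 0.60) or 4.98 points (s = 0.64). With a mortality hazard of 0.8 × 0.16 = 0.128 it is 4.68. All exceed 3.6, because deaths after a non-fatal event also count.

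**3. Different HRs.** Composite HR = s × HR(death) + (1 − s) × HR(MI/stroke). Chance of passing = Φ(ln(1.2/HR) × √1264/2 − 1.96). Death HR is 1.20 throughout.

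| MI/stroke HR (assumed) | Composite HR, s = 0.60 / 0.64 | Chance of passing |
|---|---|---|
| 1.20 | 1.200 / 1.200 | 2.5% / 2.5% |
| 1.00 | 1.120 / 1.128 | 23% / 19% |
| 0.80 | 1.040 / 1.056 | 72% / 62% |
| 0.70 | 1.000 / 1.020 | 90% / 82% |

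In the 0.80 row, an estimate at the true value has an upper limit of 1.161 or 1.179 and passes. A simulation of 3,000 trials per case, with an unadjusted Cox model, gave pass rates of 72.3% and 62.1%. The composite then differs by 1.27 or 1.77 points and deaths as first event by 5.05 or 5.23 points. All-cause death differs by the 4.8 to 5.0 points of step 2, whatever happens to MI and stroke.

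**The case against.** The strongest reply is that this is wording only. No event count, alpha, margin or decision rule uses 3.6. The sentence itself speaks of non-inferiority on the composite, and the text of Section 8.2.2 does not repeat the assurance. In the tables, 3.6 / 13 sits in the row for an HR of 1.2, so an attentive reader can see a proportional split. Mortality will also be reported separately. All of this limits the consequence, but it does not make the sentence true, since the claim is tied explicitly to a confidence limit.

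A second reply is that the high pass rates need opposite effects on death and on MI/stroke, which nothing in the documents suggests. That is fair: with a neutral effect on MI/stroke the chance of passing falls to 19 to 23%. The divergent cases are illustrations, but one possible case is enough to defeat an assurance, and step 2 needs no divergence.

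Two details also stand. The 0.64 share belongs to the maintenance setting only, so the 3.9 points it gives (0.64 × 6.06) are not evidence of an arithmetic error in 3.6. And 943 deaths is an upper case, because it treats every correction-setting event as a death. The charter of the data and safety monitoring board is not available and may hold mortality rules, but those would not supply the bound claimed here.

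**Conclusion.** The point holds. The 6.1 figure is sound as the composite difference at HR 1.20 under the planning assumptions. The 3.6 figure is at best an apportioned planning value, and the design does not assure it. Passing the composite test is compatible with an upper mortality limit of 1.22 to 1.24 at the same observed HR and, in the illustrative divergent cases, with a true death HR of 1.20 and an all-cause difference near 5 points.

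The exact sizes rest on the assumed death shares and counts, constant hazards and the 48-month schedule. That a composite-only test sets no mortality bound rests on none of them. The effect is confined to how a positive result would be read, so the text should be corrected; the design need not change.

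**What to change.** Either delete the mortality part of the sentence in the synopsis and Section 3.1.1, together with the deaths column in both tables, or keep 3.6 with a label. The label should say that it assumes a common HR of 1.20 on all components and a stated death share of first events, and that the non-inferiority test does not bound it. No other mortality figure should take its place. In either case add: the non-inferiority conclusion applies to the composite endpoint only.

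A useful but separate addition is to report the unadjusted all-cause mortality HR with its two-sided 95% confidence interval beside the primary result, without a non-inferiority claim. Section 8.2.1.2 lists adjusted Cox models for the components but no unadjusted HR.

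The cost is a few words in two places, one column or footnote in two tables and, if wanted, one extra Cox estimate. Event count, power, margin, alpha and the 6.1 figure stay as they are. The only loss is a less favourable stated assurance.
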